For the continuous study outcomes, changes from baseline to three months will be compared between the study arms using two-sample, two-sided t-tests with 5% type I error rates. Changes in QOL, number of steps, and length of stay will be compared between the two treatment sequences using two-sample two-sided t-tests. No adjustments will be made for multiple testing. Means, SDs, medians, ranges, and frequency distributions will be reported and plotted over time by study arm. Linear models will be used to assess the impact of treatment arm on three-month outcomes after adjusting for the corresponding baseline measure and other variables related to the outcome (age, degree of breathlessness at baseline using the mMRC dyspnea, and

FEV1). Repeated measures mixed models will be used to estimate the intervention effect over the 6 months of the study (this will measure trajectory and maintenance of benefits / behavior change). Intent-to-treat analyses will also be performed to determine the sensitivity of the results to dropouts and missing values. In the intent-to-treat analyses, if a month three measure is missing for any reason, it will be described as not changing from baseline. Healthcare utilization (number of ED visits, hospitalizations, and length of stay) between baseline and three months will be treated (analyzed) as both binary (for incidence rates) and continuous (for the number of events). The binary endpoints will all be compared between groups using Fisher's exact test. Logistic regression models will also be fit to look for differences in these outcomes by arm after adjusting for age, mMRC, FEV1, baseline levels of anxiety, depression, and fear, and baseline healthcare utilization, (before starting the study) particularly hospitalizations in the previous year.

Descriptive summaries of the changes between baseline, three, six, and nine months will be used to assess the effect of the home based intervention on the control arm and the residual beneficial effect on the intervention arm. These results will be only descriptive and exploratory. No formal hypothesis testing will be done. All data will be stored in REDCap and analyzed using SAS (Cary, NC).

Per-Protocol Analysis (Dose Response): We will conduct an exploratory analysis to assess the effect of dose of PR sessions on study outcomes. This analysis will control for potential confounders of dose.

Assessment of Bias: Potential bias due to loss to follow-up will be assessed using a time to event analysis for the association of patient characteristics with time to dropout; results will be reported and used to evaluate the robustness of the study findings. We will also conduct sensitivity analyses in which missing data for dropouts are imputed under plausible missing-not-at-random assumptions.

Missing data: A common affliction with randomized clinical trial field experiments is noncompliance with both treatment and missing study participation data. To estimate the overall treatment effect for the entire sample, an "intention to treat" analysis will be conducted, using our above likelihood-based analysis method for repeated measures, including data on all subjects who were randomized to the study group. This allows us to use all available data, rather than delete participants with missing values from the analysis of treatment effects.³⁴

Aim 4: Cost-Effectiveness Analysis

This aims to estimate the value of implementing Home PR compared to subjects referred to conventional PR. The CEA, will estimate the ratio of the average change of cost per patient divided by the average change in QALYs per patient for health coaching compared to delivering standard care. QALYs will be based on the EQ-5D-3L³⁵ using a preference-based value set derived from a sample of the US population. QALYs will be calculated by multiplying the utilities by a number of time participants spent in a particular health state. Transitions between health states will be linearly interpolated. The perspective for the CEA is that of the healthcare provider.

For both arms, all resource utilization at the health centers for the one-year period following index hospitalization discharge will be collected. Estimated costs will be standardized using a bottom-up approach. Professional services defined by Current Procedure Terminology code will be valued using national reimbursement amounts from the Medicare fee schedules. Billed charges for hospital services will be valued using department specific cost-to-charge ratios based on the hospital's annual Medicare cost report. All costs will be inflated to a common year using the Gross Domestic Product implicit price deflators.

Multivariate regression models will be employed to control for differences between study groups. Due to the highly skewed nature of healthcare costs, a generalized linear model incorporating a gamma distribution and log-link function will be used. The cost-effectiveness of the home PR intervention will be determined using the threshold of \$50,000/QALY. The 95% CI of the cost-effectiveness ratio will be calculated using nonparametric bootstrapping.

Healthcare utilization occurring at facilities outside of our network will not be captured. Sensitivity analysis of the cost-effectiveness will be performed based on residency status (local, regional, and distant).

Limitations: We acknowledge that comparing to completed regular PR would be ideal, however, given that the completion rate post-hospitalization is so low, accruing for such a study would be unrealistic. We strongly believe that the proposed design truly represents “a real world” study and the result from it would be applicable to the practicing clinicians and regulatory agencies and payers to further support alternative ways of PR (if our hypothesis is confirmed: increased adherence, decreased readmission and patients’ critical outcomes like daily physical activity and quality of living). We will put a dedicated effort to motivate individual to attend conventional PR if they are randomized to arm.

We will not know if the improvement in adherence is because of the home-based PR or health coaching. However, given that, only 4% complete conventional PR after a hospitalization, a meaningful improvement in adherence would not require much effort from the patients the home-based PR program.

R61 milestones (two years)

Year 1

1. Finalization of the protocol and the informed consent document
2. Development of the manual of operations and case report forms
3. Establishment of a Data and Safety Monitoring Board
4. Institutional Review Board approval of the trial
5. Pilot cohort of 10-15 patients to refine the intervention already developed for outpatients
6. Qualitative study and application of the necessary changes to the proposed Home PR

Year 2

Begin enrollment into the clinical trial to allow for an evaluation by the end of the R61 phase of early enrollment and the probability of completing the trial on time and budget. Target for year two will be to recruit 30 of 150 subjects planned for the whole study.

R33 milestones

Meeting the projected recruitment for all study participants, including women and minorities (50 subjects per year).

1. Year 3 – 80/151 subjects recruited,
2. Year 4 – 130/151 subject recruited;
3. Year 5 – 151 of 151 subjects recruited, Database lock and analysis, Submission of the primary manuscript(s) to peer-reviewed scientific journal(s) and dissemination of results including the submission of study results to ClinicalTrials.gov within 12 months of the primary completion date.
4. **All years milestones** – Report of monitoring protocol implementation and collection of data related to primary and secondary endpoints and adverse events.

BIBLIOGRAPHY

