During the consent process, the patient will have the opportunity to try the proposed home-based PR system in the hospital room, aiding in their confidence in their ability to use the system and the ease of the exercises. The study team will provide a step by step demonstration of the exercises (following the exercises on the computer tablet). The participant will be asked to rate their confidence to use the technology presented and their confidence (self-efficacy) to perform the home rehabilitation routine on a scale from 0 (no confidence) to 10

(great confidence). A rating of five or greater will be deemed an acceptable confidence level to participate in the study.

Each participant will be asked to define a particular place and time they can perform the home-based PR. The physical and mental environment is critical for the successful adoption of new behavior (PR). Participants will learn about the weekly calls with the coach to discuss their rehabilitation and monitored measures (steps, level of shortness of breath, well-being, and fatigue). They will then go over the daily answers to well-being questions (mood, breathlessness, and energy, as tested in the pilot study and shown in Fig.2; see participant software application section below). After performing the PR routine (to ensure safety and understanding) and reviewing the use of the monitors, a plan for a PR coach call, a week to 10 days after discharge. The participant will use the criterion activity monitor (Actigraph, Fig. 3) that will determine the baseline physical activity during the first week immediately after discharge to define a baseline physical activity. The coordinator will discuss the in-home activities with the participant to identify possible exercise-related fall hazards in the home environment.

[figure not shown]

Figure 2

Figure 3

Figure 4

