The primary endpoint of this study will be the rate of adherence compared between the two groups. Secondary endpoints include rates of COPD related hospitalization or death, activity levels as measured by the average number of steps per day, and the CRQ scales of dyspnea, fatigue, emotional function, physical, mastery, and the total score. Differences between groups will be compared with Fisher’s exact tests for proportions and ttests for continuous endpoints. These analyses will be supplemented with logistic regression models and linear models to compare groups after adjusting for confounding factors.

One hundred and forty-four patients will be entered on this study (72 per arm). After adjusting for multiple comparisons, this sample size will provide at least 80% power to detect a difference in the rates of adherence of 26% in the control group to 50% in the intervention group. This sample size will also provide at least 80% power for detecting a 50% reduction in hospitalization/death rates (from 50% in the control group at 6

months to 25% in the intervention group at 6 months), a difference of 1000 steps at 3 months (assuming a standard deviation [SD] of 2,000 steps), and a 0.5 difference in CRQ summary scores at 3 months (assuming an SD of 1.0). The sample size will be increased to 150 (75 per arm) to account for a 5% drop out rate.

Outcomes for the Phase 2 Randomized study

Aim 3a: Adherence will be our primary outcome

Overview: The reported adherence for PR after a hospitalization is 4% and in the best case scenario (free PR and free transportation like in the UK) is 10%. From our preliminary data, now in press (Respiratory Care), we found an adherence of >80% to the proposed system in outpatients with COPD. We hypothesize the adherence to a complete home-based PR program by post-hospitalized patients will be around 50%, and the adherence to the conventional hospital-based PR program to be 25% (due to our strong efforts to encourage people attend) will consider a complete PR when 75% of the expected PR visits are completed. We will compute the degree of completion of conventional PR from our electronic health record (EHR). The home-based PR compliance will be assessed by the entries of the PR coach in REDCap.

Aim 3b: CRQ Physical and Emotional Summary scores post PR

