Hypothesis 3a (Aim 3a) states that adherence will be higher in subject referred to home PR, will be tested with Fisher’s exact test supplemented with logistic regression adjusting for dyspnea MRC, age, social support, comorbidities, and FEV1. Exploratory analyses will be performed to examine how the number of rehab sessions impacts hospitalization/ED rates, CRQ dyspnea score, CRQ emotional score, and number of daily steps.

Hypothesis 3b (Aim 3b): participants on home-based PR will have higher physical (dyspnea fatigue) and, higher emotional CRQ summary scores at month three than participants who were referred to conventional PR. Tested with t-tests supplemented with linear regression models adjusting for baseline scores and dyspnea MRC, age, social support, comorbidities and FEV1.

Hypothesis 3 c (aim 3c): participants on home-based PR will have more daily PA than participants referred to conventional PR at month three. This will be measured by daily steps and minutes spent in sedentary, light, and moderate activity measured by the ActiGraph.^{30,31} This study has two activity monitors, the ActiGraph, a gold standard activity monitor used for outcome measures (7-day wearing) at baseline, 3, and 6 months; and the Garmin Vivofit PR activity monitor, which will be used daily, but will NOT be used as an outcome measure, rather for PR and health coaching and participant awareness of physical activity (participant will keep this activity monitor). Tested with Wilcoxon tests supplemented with linear regression models adjusting for baseline values and dyspnea MRC, age, social support, comorbidities and FEV1.

Hypothesis 3d (Aim 3d): individuals in the home-based PR program will have lower readmissions and ER visits compared to individual referred to conventional PR. Tested with Fisher’s exact test supplemented with logistic regression models adjusted for hospitalizations in the previous year, age, dyspnea, and comorbidities.

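### Daily steps have several conflicting tests and no lead analysis, so the stated power belongs to no one test; the baseline wear week is also not fixed relative to allocation

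*Combined protocol and SAP*

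**What the plan says.** **Tests.** The document describes the analysis of steps in several places.

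- *Statistical Analysis and Power* (repeated under *Data Analysis*) lists average steps per day as a secondary endpoint and gives Fisher's "exact tests for proportions and ttests for continuous endpoints". It claims at least 80% power for "a difference of 1000 steps at 3 months (assuming a standard deviation [SD] of 2,000 steps").
- *Analyses*, Hypothesis 3c, states that "participants on home-based PR will have more daily PA than participants referred to conventional PR at month three". The test is given as: "Tested with Wilcoxon tests supplemented with linear regression models adjusting for baseline values and dyspnea MRC, age, social support, comorbidities and FEV1". It does not say whether the Wilcoxon test compares levels or changes.
- *Analyses*, the paragraph on continuous outcomes, says that "changes from baseline to three months will be compared between the study arms using two-sample, two-sided t-tests with 5% type I error rates", and names steps: "Changes in QOL, number of steps, and length of stay will be compared between the two treatment sequences using two-sample two-sided t-tests". It continues: "Linear models will be used to assess the impact of treatment arm on three-month outcomes after adjusting for the corresponding baseline measure". It then adds repeated-measures mixed models over six months, and an analysis in which a missing month-3 value counts as no change from baseline.
- *Missing data* assigns the overall intention-to-treat effect to the likelihood-based repeated-measures method.

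**Baseline week.** The Phase 1 procedures in *Study Design and Methods* describe the ActiGraph as the monitor "that will determine the baseline physical activity during the first week immediately after discharge to define a baseline physical activity". *Phase 3 (R33)* randomizes the remaining 120 patients at hospital discharge and carries the R61 procedures into the home arm. For all participants, that section and Aim 3c give the timing of the first wear period only as baseline. The *Conventional PR group* section acknowledges that interventions of this kind cannot be blinded.

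**The concern.** A reader cannot tell which result will be reported as the step result. A Wilcoxon test, a t-test on change, a t-test on month-3 levels, a baseline-adjusted model and a mixed model can give different p-values from the same data. They also differ in power, so a power statement not attached to one of them cannot be checked against the planned analysis.

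The second issue is what the baseline measures. A baseline is safe to subtract or adjust for when allocation cannot have influenced it. As written, the home-arm wear week in Phase 3 comes after the patient knows the allocation. If allocation changed walking in that week, any analysis using it would carry some of that change as bias. The rule that sets a missing month-3 value to no change from baseline depends on the same week.

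**Working it through.** **Inputs from the plan.** 72 per arm; difference 1,000 steps at 3 months; SD 2,000; two-sided 5% (from the paragraph on continuous outcomes). **Not in the plan, so assumed:** the correlation rho between wear-week and month-3 steps (0.3, 0.5, 0.7), and any between-arm shift e in the wear week caused by allocation. Powers are from the noncentral t distribution.

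**Step 1: reproduce the plan's figure.** Standardized difference 1,000/2,000 = 0.5. With 72 per arm the power is 84.6%, so the claim of at least 80% holds for a t-test with that SD. A Wilcoxon test on normal data (effective n = 72 × 3/π = 68.8) has about 83%.

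**Step 2: no shift (e = 0), both readings of the SD.**

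If 2,000 is the SD of a value at one time:
- change-score SD = 2,000 × √(2(1 − rho))
- adjusted-model SD = 2,000 × √(1 − rho²)

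If 2,000 is the SD of the change:
- level SD = 2,000 / √(2(1 − rho))
- adjusted-model SD = level SD × √(1 − rho²) = 2,000 × √((1 + rho)/2)

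| Reading of SD 2,000 | Test | rho 0.3 | rho 0.5 | rho 0.7 |
|---|---|---|---|---|
| Single-time value | Month-3 level | 84.6% | 84.6% | 84.6% |
| | Change score (SD 2,366 / 2,000 / 1,549) | 71% | 85% | 97% |
| | Baseline-adjusted | 88% | 93% | 99% |
| Change | Month-3 level (SD 1,690 / 2,000 / 2,582) | 94% | 85% | 64% |
| | Change score | 84.6% | 84.6% | 84.6% |
| | Baseline-adjusted | 96% | 93% | 90% |

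The 80% thresholds: with 72 per arm and a 1,000-step difference, 80% power needs an SD no larger than about 2,127.
- First reading, change score: 1 − rho = (2,127/2,000)²/2 = 0.566, so it misses 80% when rho is below about 0.43.
- Second reading, level test: 2(1 − rho) = (2,000/2,127)² = 0.884, so it misses 80% when rho is above about 0.56.

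The baseline-adjusted model stays above 80% under both readings.

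**Step 3: timing of the wear week.** Randomization at discharge, plus a baseline in the first week after discharge, puts the home-arm baseline after allocation for the 120 Phase 3 patients. The documents do not state the control-arm wear timing, the randomization time of the first 30 patients, or the day home exercise starts.

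**Step 4: what a shift would do (hypothetical).** Suppose the home arm is e steps higher in the wear week because of allocation. The change score is off by −e, the adjusted model by about −rho × e, and a month-3 level comparison by 0. For a true difference of 1,000, rho = 0.5, and SD 2,000 (both readings coincide at this rho):

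| Assumed e | Change score: estimate, power | Adjusted: estimate, power |
|---|---|---|
| 0 | 1,000, 85% | 1,000, 93% |
| 250 | 1,000 − 250 = 750, 61% | 1,000 − 125 = 875, 85% |
| 500 | 1,000 − 500 = 500, 32% | 1,000 − 250 = 750, 73% |

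With e = −250 the estimates would be 1,250 and 1,125, an overstatement. Nothing in the documents fixes e or its sign.

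**The case against.** **The texts may be less at odds than they look.** The t-test for continuous endpoints is a general statement, which the later paragraph can be read as specifying as a change score. The *Missing data* section gives the overall intention-to-treat effect to the repeated-measures method, the nearest the plan comes to a lead analysis. Both points are fair. But Wilcoxon against t-test on change remains for the same outcome, and nothing says the repeated-measures model leads for steps.

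**The timing argument is an inference.** The post-discharge week is described for the unrandomized pilot and reaches the trial through one clause in *Phase 3 (R33)*. The first coach call is planned a week to 10 days after discharge, and the provider is contacted before the program starts; both fit a run-in week with no exercise. The exercise demonstration is part of the consent process, so future controls may try the routine too, and both arms receive the same Garmin. A reader might infer that the wear week is contaminated by home exercise and that the benefit will be understated. The documents do not support that: they show neither an early effect nor its direction. What stands is only that a baseline after open allocation is not protected from such an effect.

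**The level comparison is not clearly better.** With no shift, the adjusted model has more power under either SD reading. At rho = 0.5, with 2,000 as a single-time SD, that remains so until e reaches about 268 steps. This stands: the choice is a trade-off between bias and power that depends on the timing.

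**Conclusion.** The plan does not define one main analysis of daily steps, and its power statement cannot be tied to one. This follows from the text and needs no assumption about the wear week. A reader might conclude that the trial is underpowered for steps. That is not shown: the stated figure reproduces, and a shortfall arises only for particular combinations of test, SD meaning and correlation. It affects the change score if 2,000 is a single-time SD and rho is below about 0.43, and the level test if 2,000 is the SD of change and rho is above about 0.56.

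The change-score t-test is the weakest candidate for the main test. With no shift, the adjusted model has more power under both readings over the range examined. With a shift, the change score carries all of it and the adjusted model only about rho times it.

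As written, the home-arm baseline week follows open allocation for 120 of the 150 patients' phase of recruitment. Any resulting bias is possible, of unknown size and sign, and every figure for e is hypothetical. The point should be corrected, but it concerns a secondary outcome and leaves the primary adherence endpoint untouched.

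**What to change.** 1. Do not use the t-test on change from the wear week as the main step test.
2. Name one main analysis of month-3 mean daily steps. If the wear week is confirmed to precede allocation, or to be unaffected by it, use the baseline-adjusted linear model (or the repeated-measures model evaluated at month 3). Otherwise use the month-3 level comparison, adjusted only for covariates recorded before randomization. Keep the alternative and the Wilcoxon test as sensitivity analyses.
3. Reconcile the Phase 1 procedures, *Phase 3 (R33)* and Aim 3c on when the wear week falls in each arm, and for the first 30 patients, relative to allocation and program start. Report wear-week steps by arm.
4. State whether the SD of 2,000 is of the month-3 value or of the change, and restate the power for the named test.

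**Cost.** SAP wording only, with no change to treatment, visits or allocation. If the level comparison is chosen and there was no early shift, some power is given up: 84.6% against 88% to 99% for the adjusted model over rho 0.3 to 0.7, when 2,000 is a single-time SD. If 2,000 is the SD of the change, the level test falls below 80% once rho exceeds about 0.56, so item 4 should be settled before the choice is final.

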Phase 3 (R33): Mayo Clinic Rochester and Jacksonville Fl will participate in this Phase. After review of the first 30 participants, the remaining 120 patients with a COPD-related hospitalization (exacerbation or pneumonia) will be randomized at hospital discharge to the home-based PR or usual care (referral to conventional center-based PR). Inclusion, exclusion criteria and recruitment will be identical to the Phase 1 and 2 of the study. Randomization will be completed online through a centralized program Research Electronic Data Capture (REDCap).

The participants randomized to home-based PR will follow the same procedures in the R61 phase, plus any changes suggested by the qualitative study. Any changes will involve a protocol modification and submitted to the IRB for review.

Questionnaires and Activity Monitor: All participants will be asked to complete questionnaires and wear a small activity monitor (Actigraph) at Baseline and Months 3,6 and 12. The participants will be supplied with postage paid envelopes to return the questionnaires and activity monitor.

Questionnaires: Questionnaires include the Medical Research Council (MRC), Chronic Respiratory Questionnaire (CRQ), EuroQol-5D (EQ5D), Patient Health Questionnaire- 9 question (PHQ9), General Anxiety Disorder – 2 question (GAD2), Interpersonal Support Evaluation List (ISEL), Self-Management Ability Scale (SMAS30), Linear Analog Scale Assessment (LASA), Meaning in Life Questionnaire (MIL) and the Working Alliance Inventory (WAI). All questionnaires with the exception of the WAI will be administered at baseline and 3, 6 and 12 Month. The WAI questionnaire will be administered when the participant has completed the Health Coaching Period. For participants randomized to the Intervention arm, the WAI will be administered at 3 months. Participants randomized to the Control/Wait arm will receive the WAI at 6 months. The Charlson Comorbidity Index (CCI) will be included in the baseline questionnaire packet. The CCI will assist in summarizing the enrolled subjects in statistical models.

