The PHQ9 will be reviewed by study staff within 24 hours of receiving the questionnaire in the mail. The study staff will score the PHQ9 and a total score >14 (15 and above) and Item 9 is a zero will prompt a review of medical records for current mental health treatment (in consultation or pharmaceutically) of depression. If the patient is not being treated for mental health issues a licensed health care provider will contact the patient and offer a referral or other treatment suggestions. If anything other than “not at all” on Item 9 “Thoughts that you

would be better off dead or of hurting yourself in some way? The participant will be called by a licensed health care provider.

Health Care Utilization: The Study Coordinator will contact all participants at Months 3,6 and 12 via telephone to determine health care utilization, the participants will be asked how many times they have gone to the doctor/Emergency Room/Hospital for breathing problems. In addition, the participants will be asked if they have taken antibiotics or prednisone for breathing related illnesses since the last time the Study Coordinator called them.

Conventional PR group: Referral to Conventional PR (retention strategies)

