To determine the effect size of the home-based PR system with health coaching on physical and emotional QOL, we will analyze the CRQ physical and emotional summary scores. The CRQ Physical Summary score includes dyspnea (symptom #1 in COPD) and fatigue (symptom #2 in COPD) domains; the CRQ Emotion Summary score, includes the emotion (independent factor for admissions and poor quality of life) and mastery (self-management) domains of the CRQ.²⁵ The CRQ is a 20-question inventory assessing the areas of dyspnea, fatigue, emotion, and feelings of mastery. The fatigue, emotion, and mastery subscales ask patients to rate how often in the last two weeks they have been afflicted with a particular feeling or experience on a scale of 1 to 7, with higher ratings indicating less symptom impairment. The CRQ has shown to be valid and has high internal consistency reliability.²⁵ Test-retest reliability is adequate in all subscales, but is particularly high in the subscales of fatigue ($r=0.90$), emotion ($r=0.93$), and mastery ($r=0.91$).²⁵ The minimal clinically important difference for this instrument of 0.5 points is universally recognized.¹³ The CRQ will be measured at baseline, and 3, and 6 months post-hospital discharge.

Aim 3 c: Daily Physical activity post PR

Physical activity is the strongest predictor of survival in COPD and is independently related to hospitalization.^{26,27} Physical activity will be measured by the ActiGraph™ wGT3X-BT activity monitor (Fig. 8), which has been validated and used to assess physical activity in COPD populations.²⁷⁻²⁹ The ActiGraph activity monitor has tri-axial accelerometers and will be worn on the wrist for seven days at baseline and at 3, and 6 months post-hospital discharge at the pre-specified time points (Figure 17) and will measure steps and minutes spent in sedentary, light, and moderate activity.^{30,31} **The main daily physical activity outcome is the number of daily steps (most common, generalizable and simple).** Secondary, but important, measures to be analyzed are activity counts, minutes per day spent in daily physical activities of at least moderate intensity, and sedentary time (<2METs metabolic equivalents).³² We will also measure sleep time and sleep efficiency with this monitor.

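### The PHQ-9 review limit starts at postal receipt, and nothing tells the patient to post the form before the monitor's wear week ends, so a non-zero Item 9 answer can wait unread

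*Combined protocol and SAP*

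**What the plan says.** The paragraph on the PHQ-9 that follows the Questionnaires list in the combined protocol and SAP sets one time limit: "The PHQ9 will be reviewed by study staff within 24 hours of receiving the questionnaire in the mail". Any Item 9 answer other than the lowest category leads to a telephone call from a licensed provider. No time is attached to that call.

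The Questionnaires and Activity Monitor paragraph puts the form and the monitor on one schedule: "All participants will be asked to complete questionnaires and wear a small activity monitor (Actigraph) at Baseline and Months 3,6 and 12". It gives one return route: "The participants will be supplied with postage paid envelopes to return the questionnaires and activity monitor".

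Aim 3c gives the wear time of the ActiGraph, which "will be worn on the wrist for seven days at baseline and at 3, and 6 months post-hospital discharge". The Methods text on the pilot phase places baseline wear after the patient has gone home, with a monitor "that will determine the baseline physical activity during the first week immediately after discharge".

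The Health Care Utilization paragraph adds a live contact: "The Study Coordinator will contact all participants at Months 3,6 and 12 via telephone to determine health care utilization". The questions listed for that call concern visits, admissions, antibiotics and prednisone. Item 9 is not among them.

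**The concern.** The protocol itself treats a non-zero Item 9 as something a licensed provider must follow up. What matters for the patient is the time from giving the answer to someone reading it. The plan limits only the last part of that time, after the envelope arrives. The earlier parts, from completion to posting and from posting to arrival, have no limit.

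The first of these could be long. A patient who has a questionnaire packet and a monitor to wear for a week may well fill in the forms early and send everything back together.

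The same protocol handles abnormal oximetry and heart-rate readings differently: they are transmitted electronically, and the principal investigator is alerted by text message within 24 hours. Nothing comparable links the self-harm answer to its reader. At stake is participant safety in both arms. Sample size and power are not affected.

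**Working it through.** No figure in the plan gives the time from answer to reading, so there is none to reproduce. The only stated figure is the 24 hours from receipt.

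Inputs:
- Review time after receipt, R: 0 to 1 day (PHQ-9 paragraph).
- Monitor wear: 7 days, stated for baseline, month 3 and month 6 (Aim 3c). Month 12 is on the schedule, but no wear length is given for it.
- Mail time, M: not in the documents. Assumed to be 2 to 5 days, with 1 to 7 days as a wider range.
- Time the form is held before posting, H: not limited by the documents. Two cases are used, 0 days and the full 7 days of wear.

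Formula: age of the answer when read = H + M + R.

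| Case | Mail 2–5 days | Mail 1–7 days |
|---|---|---|
| Posted at once, or completed on the last day of wear and then posted (H = 0) | 0 + 2 + 0 = 2 to 0 + 5 + 1 = 6 days | 0 + 1 + 0 = 1 to 0 + 7 + 1 = 8 days |
| Completed at the start of wear, returned with the monitor (H = 7) | 7 + 2 + 0 = 9 to 7 + 5 + 1 = 13 days | 7 + 1 + 0 = 8 to 7 + 7 + 1 = 15 days |

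The second row is not an upper bound, because no return deadline is stated. It shows what an ordinary way of following the instructions could produce.

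Forms involved: 150 patients × 4 time points = up to 600 PHQ-9 forms come back by post. The seven-day wear is stated for three time points, so the second row has support in the text for at most 150 × 3 = 450 of them. These are counts of forms. The documents give no rate of non-zero Item 9 answers, so the number of delayed positive answers cannot be estimated.

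Other contacts, as described, do not close the gap. The tablet's daily questions cover mood or well-being, breathing and energy, and belong to the home programme. The weekly coaching calls are also part of that programme. The control group receives an encouragement call two weeks after discharge. The calls at months 3, 6 and 12 ask about health care use. None of these is described as asking Item 9.

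**The case against.** Several stronger readings are tempting, and the documents do not support them.

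- A reader might infer that the plan breaks its own 24-hour promise. It does not. The limit is openly counted from arrival of the form, and setting 9 to 13 days against 24 hours compares two different intervals.
- A reader might infer that the usual delay exceeds a week. That needs early completion, holding the form for the monitor, and the assumed mail time, all together. The text mentions envelopes in the plural and never says that form and monitor share one.
- A reader might infer that patients who do not return a packet are never screened. A missing packet loses that time point's form, one of four.
- A reader might treat the absence of a time limit on the provider's call as a design fault. It is missing detail. The milestones list a manual of operations and case report forms, which may hold both that timing and the return instructions, and they cannot be seen here.

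A further objection concerns the remedy of giving the PHQ-9 in hospital or by telephone. This has real costs. It changes self-completion to interview and, in hospital, the setting and timing of baseline. The utilization models in the Analyses section adjust for baseline depression, and the PHQ-9 is the only depression-specific instrument listed, so it is the likely source of that covariate. Aim 3d has the utilization calls made from a script by a coordinator blinded to the intervention, and a depression interview would lengthen them and might affect the blinding.

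These objections stand and limit the point. They do not remove it: as written, nothing limits how long a completed form may wait before it is posted.

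**Conclusion.** The point holds as a gap in the return procedure, not as an internal contradiction. The one stated limit begins at receipt, the form shares its schedule and postal route with a monitor worn for a week, and no instruction separates the two. With an assumed 2 to 5 days' mail, an Item 9 answer is 2 to 6 days old when read if the form is posted promptly. It is possibly 9 to 13 days old if the form is completed early and kept for return with the monitor. The longer range should be read as possible, not usual, and as supported by stated wear times at three of the four time points. It rests on the mail-time assumption and on how the patient handles the packet. The manual of operations might already settle that second matter. The improvement is cheap enough to make without waiting for evidence of actual delays.

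**What to change.** In the Questionnaires and Activity Monitor paragraph and the PHQ-9 paragraph, state that the patient dates the PHQ-9 and returns it on the day of completion, in its own postage-paid envelope separate from the monitor, in the same way in both arms. This keeps self-completion and takes the wait of up to seven days out of the interval; the mail time remains. The patient's date also lets the trial measure the delay that it currently cannot see.

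Use the existing calls at months 3, 6 and 12 to prompt for a form that has not arrived. A reminder does not require the caller to know the arm. The Health Care Utilization paragraph lists no baseline call, so the protocol should also say who follows up a missing baseline form.

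The cost is one extra envelope per time point (at most 150 × 4 = 600 in all) and a short amendment.

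Giving the PHQ-9 in hospital or by telephone is an option for the sponsor to weigh against mode effects, the baseline depression covariate and the blinded call. The timing and content of the provider's response to a non-zero Item 9 are for the sponsor to define.
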